05.Jan.2018

Efficacy of Wet Cupping on Reactive Oxygen Species and Antioxidant Capacity:A Self-controlled Interventional Study

STUDY PROTOCOL

Among the healthy individuals who applied for Wet Cupping Therapy (WCT) to Traditional and Complementary Therapies (TCT) center in Karabuk Medical Faculty Education and Research Hospital, 24 individuals were enrolled in the study. Individuals who had a chronic disease, use medication everyday and have conditions contraindicated for WCT (such as (Hgb<9,5;INR>1,2) were excluded.

Informed consent was obtained from all the individuals participated in the study. Ethical approval was granted by Karabuk University Clinical Trials Ethics Committee with number 1/5 and date 09.01.2018.

All patients underwent three sessions of Wet Cupping Treatments (WCT), at one month intervals consecutively (0 days, 30 days, and 60 days). WCT was performed using disposable vacuum cups on 5 acupuncture point locations: DU 14 (Dazhui) point on the posterior median line, in the depression below the processus spinosus of the 7th cervical vertebra; UB 42 (Pohu) points bilaterally on the back, 3.0 cun lateral to the lower border of the spinous process of the 3rd thoracic vertebra interscapular region; and UB 46 (Geguan) points bilaterally on the back, 3.0 cun lateral to the lower border of the spinous process of the 7th thoracic vertebra ([Figure 1](#)). Each WCT procedure took about 20 min and was conducted in 5 phases:

Sterilization: The selected regions is disinfected with povidone iodine before the procedure.

Primary sucking: The cup is placed on the selected sites and the air is withdrawn from inside the cup by manual suction. The cups are located on the skin and left for a period of 3 to 5 minutes.

Scarification: Superficial incisions, 2–3 mm in depth and 3–5 mm in length, are made on the skin using a number 15 sterile surgical blade.

Blood-letting by secondary sucking: The cups are located on the skin again, in the same manner as described above, and left until filled with blood from the capillary.

Disconnection and dressing: The cups filled with blood are removed and destroyed as medical waste. A dressing with sterile sponge is applied.

The individuals venous blood samples obtained initially and after the completion of the three consecutive application will be evaluated in terms of Reactive Oxygen species and Antioxidant capacity. In addition samples from the cupping blood during the first and the third WCT application will also be obtained and evaluated in the same manner. Total antioxidant status(TAS),total oxidant status (TOS),super oxide dismutase (SOD),catalase (CAT) levels will be measured biochemically in all samples.

**05.Jan.2018**

## **Efficacy of Wet Cupping on Reactive Oxygen Species and Antioxidant Capacity:A Self-controlled Interventional Study**

### **Statistical Analysis**

Conformity to normal distribution of the data will be assessed with the Kolmogorov-Smirnov test. In groups showing normal distribution, the Student's t-test will be used in the comparison, Friedman test will be used for groups showing abnormal distribution. For paired groups showing normal distribution Paired t test, for groups showing abnormal distribution Conover test will be used. A value of  $p < 0.05$  will be accepted as statistically significant

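### The Student's t-test rule fits no comparison in a study where every sample comes from the same 24 people; it is mismatched with Friedman, and no comparison is assigned a test

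*SAP*

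**What the plan says.** The title calls the trial "A Self-controlled Interventional Study". The Protocol reports that "24 individuals were enrolled in the study", and everyone receives the same three sessions. It describes two venous samples per person ("The individuals venous blood samples obtained initially and after the completion of the three consecutive application") and two cupping-blood samples, from the first and third sessions. TAS, TOS, SOD and CAT are measured in every sample. No comparator arm or between-person subgroup is described.

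The SAP's Statistical Analysis section begins with a normality check: "Conformity to normal distribution of the data will be assessed with the Kolmogorov-Smirnov test". Two rules follow.

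- **Rule 1, groups.** If normal: "In groups showing normal distribution, the Student's t-test will be used in the comparison". If not: "Friedman test will be used for groups showing abnormal distribution".
- **Rule 2, paired groups.** If normal: "For paired groups showing normal distribution Paired t test". If not: "for groups showing abnormal distribution Conover test will be used".

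The significance threshold is 0.05. Neither rule is linked to a marker, a time point or a blood source.

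**The concern.** There are three linked problems.

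1. **No independent groups exist.** Because the paired t-test has its own rule, the Student's t-test in rule 1 reads most naturally as the independent-samples test. Nothing in the described design calls for one. If the paired form was meant, rule 1 merely repeats rule 2.
2. **Rule 1 does not match itself.** Student's t in its unpaired form assumes independent samples, whereas Friedman needs matched blocks. If Friedman is meant for more than two related samples, no corresponding method for normal data is named.
3. **Nothing is mapped.** All the data are paired, so normally distributed data can be placed under either rule, and the choice could be made after the results are known. The SAP also does not say whether normality is judged on the raw values or on the within-person differences; the paired t-test depends on the differences.

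At stake are the standard error, and hence the type I error and power, if an analyst follows rule 1 literally.

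**Working it through.** The documents contain no power or error-rate calculation, so there is no stated figure to reproduce.

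**Inputs.** From the documents: n = 24, four samples per person, four markers, threshold 0.05. Assumed, because the documents do not give them: two-sided testing, within-person correlation r from -0.3 to 0.7, and a shift of 0.6 SD.

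**Number of comparisons.** The two before/after contrasts (venous; cupping session 1 vs 3) give 4 markers × 2 = 8. Four samples form 6 pairs, so all pairs give 4 × 6 = 24, an upper bound. None is assigned a test.

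**(a) Unpaired test applied to paired normal data.** With unit SD, the variance of the mean difference is 2(1 - r)/24. The unpaired test takes it to be 2/24. The ratio of unpaired to true standard error is therefore 1/√(1 - r). At r = 0.5 this is 1/√0.5 = 1.41.

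Error rates come from 200,000 bivariate-normal simulations per cell, with the pooled t-test (46 df) and the paired t-test (23 df) run on the same data:

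| r | SE ratio | Type I error, unpaired | Power, unpaired | Power, paired |
|---|---|---|---|---|
| -0.3 | 0.88 | 8.5% | 52.6%* | 41.5% |
| 0 | 1.00 | 4.9% | 53.0% | 51.2% |
| 0.3 | 1.20 | 2.0% | 53.7% | 66.4% |
| 0.5 | 1.41 | 0.7% | 54.4% | 80.4% |
| 0.7 | 1.83 | 0.1% | 55.4% | 95.3% |

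*Not a fair comparison, because the type I error is inflated.

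The paired test holds about 5% type I error at every r. With a 0.5 SD shift instead (100,000 simulations), power at r = 0.5 is 36% unpaired against 65% paired, so the pattern does not depend on the choice of 0.6.

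**(b) Non-normal rules applied to only two samples, no ties.** If m of 24 people increase, the Friedman statistic is (2m - 24)²/24 on 1 df.

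- m = 17: (34 - 24)²/24 = 4.17, p = 0.041, so it rejects.
- m = 16: (32 - 24)²/24 = 2.67, below the 5% cut-off of 3.84, so it does not reject.
- Exact type I error: 2 × P(Bin(24, 0.5) ≤ 7) = 6.39%. This needs no assumption about r.
- The exact two-sided binomial p-value at m = 17 is 0.064, against the 0.041 that the chi-square form reports.

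The SAP does not say which Conover procedure it means. If it is the one that follows Friedman (23 df), p is 0.038 at m = 17 and 0.103 at m = 16, so the rejection region is the same. With two samples, both procedures use only the direction of each person's change and ignore its size.

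The exact Wilcoxon signed-rank test (critical value W ≤ 81) has type I error 4.91%. For lognormal data with log SD 1 and log shift 0.6 (200,000 simulations), power is:

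| r | Friedman | Wilcoxon |
|---|---|---|
| -0.3 | 34.1% | 37.5% |
| 0 | 41.4% | 45.1% |
| 0.3 | 53.8% | 57.8% |
| 0.5 | 67.2% | 71.2% |
| 0.7 | 86.4% | 89.4% |

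Friedman thus has 3 to 4 points less power, despite its larger type I error.

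**The case against.** The SAP never calls the Student's t-test independent or unpaired. It names a paired t-test for paired groups, and a specific rule would ordinarily override a general one. On that reading every normal-data comparison described gets the right test and the Student's clause is merely surplus. The figures in (a) need the other reading plus an assumed correlation. With r above 0 the error is conservative, costing power without adding false positives; inflation needs a negative r, which nothing in the documents supports. Part (b) needs Friedman to be run on two samples, whereas Friedman across all four followed by Conover for pairs would be a coherent plan, and ranks across four samples carry more than direction of change.

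Most of this stands as a limit on the size of the problem. A valid paired test is named, unpaired use is not shown to be intended, and (b) applies to two samples only. It does not remove the defect: the Student's clause still has no comparison it fits, it still covers the same data as the paired rule, and no other section says which rule governs. The four-sample reading of Friedman also leaves its normal-data counterpart missing.

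**Conclusion.** The concern holds. Rule 1 does not fit the described design, its two halves are not counterparts, and none of the 8 before/after comparisons (or up to 24 pairwise ones) is assigned a test. Confidence is high on these points because they rest on the documents alone.

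Actual harm is conditional. If the unpaired test were used, its standard error would be wrong unless r is 0: too large when r is positive, too small when it is negative. Over the assumed range of r, type I error runs from 8.5% down to 0.1%, with substantial loss of power at moderate or high positive r and almost no effect at r = 0. The 6.4% type I error for two-sample Friedman is exact, but assumes two samples, no ties and the chi-square p-value. Extending it to Conover assumes the post-Friedman procedure. This should be fixed; it does not show that a wrong analysis is intended.

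**What to change.** Amend the SAP's Statistical Analysis section as follows.

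- Delete the Student's t-test clause.
- List each two-sample comparison by sample and marker: venous before vs after, and cupping session 1 vs session 3, each for TAS, TOS, SOD and CAT. State whether venous vs cupping blood is planned and, if so, list it too.
- Assign each comparison the paired t-test on within-person differences, with normality judged on those differences, or otherwise a named paired non-parametric test suited to two samples, such as Wilcoxon signed-rank.
- Keep Friedman only if more than two samples are compared jointly. In that case name a repeated-measures analysis as its normal-data counterpart and state that Conover is the post-hoc test after Friedman.

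The cost is SAP wording only; no new data are needed.

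### The Conover test for non-normal paired data is not defined, and on the readings left open it does not reliably hold the 5% level

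*SAP*

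**What the plan says.** The SAP consists of one section, Statistical Analysis. It first sets a normality check: "Conformity to normal distribution of the data will be assessed with the Kolmogorov-Smirnov test". For the first kind of comparison it names Student's t-test for normal data, and otherwise "Friedman test will be used for groups showing abnormal distribution". For paired data it says "For paired groups showing normal distribution Paired t test, for groups showing abnormal distribution Conover test will be used". Significance is p<0.05 throughout. It gives no statistic, no set of samples to be ranked, no requirement for a significant Friedman test first, and no adjustment of p values.

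The Protocol's opening paragraph says that "24 individuals were enrolled in the study". Its last paragraph describes "venous blood samples obtained initially and after the completion of the three consecutive application" and adds that "samples from the cupping blood during the first and the third WCT application will also be obtained and evaluated in the same manner". Each person therefore gives four samples, two venous and two of cupping blood, and four markers (TAS, TOS, SOD, CAT) are measured in each.

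**The concern.** More than one test goes by the name Conover. Because the SAP names Friedman just before it, the likeliest meaning is the pairwise t-type test on Friedman within-person ranks. That test has a pooled error term, so its result for one pair depends on every sample that was ranked. The SAP does not say whether two or four samples are ranked together.

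Venous before versus after is the central comparison in a self-controlled study. For any marker sent to the non-normal branch, two analysts could follow the SAP faithfully and reach opposite conclusions from the same venous values. With four samples ranked, the answer also depends on cupping-blood values that do not bear on the venous question. The error can go either way: a false change declared too often, or a real one missed.

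**Working it through.** **Inputs.** From the documents: n=24, threshold 0.05, two venous and two cupping samples per person. Assumed, because the documents are silent: two-sided testing, no ties, 24 complete sets, unadjusted p values, and all cupping-venous differences and correlations. The plan's own figure to reproduce is the 5% level.

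**Two samples ranked (k=2).** With s increases among n people,

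T = |2s−n| / (2√(s(n−s)/(n−1))), referred to t with n−1 df.

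This is a sign test with a t approximation.

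- At s=17, n=24: T = 10/(2√(17×7/23)) = 10/4.55 = 2.20, above the critical 2.07.
- At s=16: T = 8/(2√(16×8/23)) = 8/4.72 = 1.70, not significant.
- The test rejects at s≤7 or s≥17. The exact binomial level is 6.39%.
- The level moves with the number of complete pairs: 3.5% at n=23, 4.3% at n=25.
- Requiring a significant Friedman test on the same two samples changes nothing. Q=(2s−n)²/n is 100/24 = 4.17 at s=17, above 3.84, and the two rejection regions coincide for every n from 18 to 28.

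**Four samples ranked (k=4).** With rank sums Rj, A the sum of squared ranks and B = ΣRj²/n,

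T = |R1−R2| / √(2n(A−B)/((n−1)(k−1))), referred to t with (n−1)(k−1) = 69 df (critical 1.99).

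A is 30×24 = 720. The standard error that the formula uses can be set against the true null SD of R1−R2:

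- *Four exchangeable samples.* Each Rj has mean 60 and variance 24×1.25 = 30, so B averages 4×(3600+30)/24 = 605 and A−B averages 115. The formula gives √(48×115/69) = 8.94. The true SD is √(24×20/6) = 8.94. They agree, and the level is about 5%.
- *Full separation, cupping pair unchanged.* Venous samples take ranks 1–2 and cupping samples ranks 3–4 in everyone. At an even split the rank sums are 36, 36, 84, 84, so B=696 and A−B=24. The formula gives √(48×24/69) = 4.09, but each person contributes ±1 to R1−R2, so the true SD is √24 = 4.90. With the cupping direction independent of the venous direction, the exact level is 15.2% (9.3% at n=23; 8.1–15.2% for n from 18 to 28).
- *Full separation, cupping samples always in the same order.* At a 15:9 venous split the rank sums are 39, 33, 72, 96, so B=708.75 and A−B=11.25. The formula gives √(48×11.25/69) = 2.80 against the same true SD of 4.90. T = 6/2.80 = 2.14, so the test rejects from 15 of 24. The exact level is 30.7% (21.0% at n=23; 16.7–32.7% for n from 18 to 28).

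Between these limits, the level was simulated for a truly null venous pair at n=24, with 100,000 multivariate normal datasets per cell and both cupping samples shifted equally:

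| Correlation (venous / cupping / cross) | 0 SD | 1 SD | 2 SD | 4 SD |
|---|---|---|---|---|
| 0 / 0 / 0 | 5.0% | 5.7% | 7.7% | 14.6% |
| 0.5 / 0.5 / 0.5 | 5.1% | 6.3% | 10.3% | 15.1% |
| 0.8 / 0.8 / 0.8 | 5.1% | 8.1% | 15.0% | 15.0% |
| 0.7 / 0.7 / 0.3 | 2.3% | 3.5% | 7.8% | 15.0% |
| 0.8 / 0.5 / 0.5 | 2.1% | 3.7% | 9.8% | 15.1% |
| 0.9 / 0.3 / 0.3 | 0.7% | 1.6% | 6.4% | 15.1% |

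A prior significant Friedman test lowers only the 0 SD column (equal correlations to about 1.9%, the last row to about 0.2%). At 1 SD or more it changes no cell by over 0.1 point, because the cupping shift itself makes Friedman significant.

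**Comparators on the venous pair alone, n=24.** The exact Wilcoxon signed-rank test rejects at W≤81, level 4.9%, and stayed at 4.7–5.1% in every simulated cell. The exact sign test rejects at s≤6 or s≥18, level 2.3%. Wilcoxon needs symmetric differences under the null. With skewed differences of median zero its level is 7.5% (lognormal, log-SD 0.5), 11.5% (exponential) or 12.9% (lognormal, log-SD 1), against 6.4% for the k=2 Conover test.

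**The case against.** The SAP does not present Conover as a follow-up to Friedman. It sets Friedman opposite Student's t-test and Conover opposite the paired t test, and that parallel favours ranking only the two samples compared. On that reading the excess is 6.4% against 5%, and at 23 or 25 pairs the test is conservative. The large figures need four samples ranked together and an assumed cupping-venous difference; several cells are near or below 5%, and 30.7% needs full separation with a fixed cupping order. A Bonferroni adjustment over the six pairs would bring most cases below 5%. Finally, Wilcoxon can itself exceed 5% with skewed differences, in a branch reserved for non-normal data.

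Much of this stands as a limit on size. The link to Friedman is an inference, the k=2 excess alone would be a minor note, and the k=4 figures show what could happen rather than what is likely. It does not remove the point. No sentence settles which samples are ranked. The SAP states no adjustment, and Bonferroni still leaves 15.2% when the cupping order is fixed. Wilcoxon's weakness concerns the shape of the venous differences themselves, not samples outside the comparison, and the exact sign test covers it.

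**Conclusion.** The concern holds, and the SAP should be changed. The test is undefined, and under the Friedman-rank reading it does not reliably hold 5%. With two samples ranked, the level is 6.4% at n=24, assuming only complete untied pairs and two-sided testing. With four ranked, it may lie well below or well above 5%, depending on correlations, the cupping-venous difference and whether the cupping pair changes. It is about 5% when all four samples are exchangeable, so the test is not always inflated.

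Confidence is moderate: the reading is inferred, the documents give no cupping or venous data, and possibly no marker enters this branch. All figures are for one marker and one comparison. Multiplicity across markers and selection by the normality pre-test are not counted.

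**What to change.** Replace the Conover test with one test named in advance. Suggested text: *For each listed pair (primarily venous before versus after), the two-sided exact Wilcoxon signed-rank test on within-person differences will be used, using only the two samples being compared, with the Hodges-Lehmann estimate and its 95% confidence interval.* State the assumption: before and after are exchangeable under the null, or the differences are symmetric. For every marker in this branch, also report the exact sign test with the median change and its 95% confidence interval, as a prespecified sensitivity analysis and not as a switch chosen after seeing the data.

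The cost is SAP wording; no new data are needed. No general gain in power is claimed. At n=24, with normal differences and an assumed 0.6 SD shift, power is 79% for Wilcoxon, 67% for k=2 Conover (at its 6.4% level) and 50% for the exact sign test. With Laplace differences and a 0.4 SD shift it is 58%, 63% and 46%.

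### The paired test is chosen by a Kolmogorov-Smirnov check that never mentions within-person differences, and the fallback is an undefined Conover test that costs power on one reading and can inflate false positives on another

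*SAP*

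**What the plan says.** The protocol's title calls the trial "A Self-controlled Interventional Study", and its opening paragraph states that "24 individuals were enrolled in the study". Its closing paragraph sets out four samples per person. Two are venous: "The individuals venous blood samples obtained initially and after the completion of the three consecutive application will be evaluated". Two are cupping blood: "samples from the cupping blood during the first and the third WCT application will also be obtained". Four markers are read from each sample (TAS, TOS, SOD and CAT): their "levels will be measured biochemically in all samples".

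The SAP (Statistical Analysis) first says: "Conformity to normal distribution of the data will be assessed with the Kolmogorov-Smirnov test". For comparisons that it would otherwise make with Student's t-test, "Friedman test will be used for groups showing abnormal distribution". For paired comparisons the rule is: "For paired groups showing normal distribution Paired t test, for groups showing abnormal distribution Conover test will be used". The threshold is p < 0.05, with sidedness not stated. Neither document mentions a difference or change within a person as the quantity to be checked or tested, and neither says which Conover procedure is meant or on how many samples it is run.

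**The concern.** Each before/after contrast compares two samples from the same person. The paired t-test needs the differences to be roughly normal; the levels need not be. A check on the levels can therefore fail in both directions. Skew between people, which cancels in the differences, can push a comparison away from the t-test for no reason. Skewed differences can also pass unnoticed behind normal-looking levels.

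The fallback matters as much as the check. Conover's name is attached to more than one rank procedure, and the one usually linked to Friedman is built for several samples per person. On two samples it discards the size of each change. On four samples, a before/after result depends partly on the other two samples. With 24 people and no sample-size justification, neither avoidable power loss nor an uncontrolled error rate is welcome.

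**Working it through.** The plan gives no power, effect size or SD, so there is no figure of its own to reproduce. Inputs from the documents: n = 24 pairs, alpha 0.05, four samples per person. Assumptions: two-sided testing; no ties; Conover means the post-Friedman rank comparison; the distributions stated below. The effect is 0.597 SD of the differences, chosen to give paired t 80% power (noncentrality 0.597 × √24 = 2.92, critical t 2.069 on 23 df).

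**1. What the check looks at.** In 2,000 simulated trials per setting, the share called non-normal was:

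| Setting | Check on the two samples: plain K-S / Lilliefors | Check on differences: plain K-S / Lilliefors |
|---|---|---|
| Lognormal people (log-SD 1), normal differences | 31% / 87% | 0% / 6% |
| Normal levels (SD 3), exponential differences | 0% / 9% | 6% / 67% |

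**2. Conover on the two samples compared.** Let b be the number of people whose value rose. With two samples:
- Friedman χ² = (2b − n)²/n
- Conover |t| = |2b − n| / √[(n² − (2b − n)²)/(n − 1)]

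Both depend on b alone.
- b = 17: χ² = 100/24 = 4.17, p = 0.041; t = 10/√(476/23) = 2.20, p = 0.038.
- b = 16: χ² = 64/24 = 2.67, p = 0.102; t = 8/√(512/23) = 1.70, p = 0.103.

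So the test rejects from 17 of 24 rises (or falls). Exact size is 2 × P(B ≥ 17 | p = 0.5) = 6.4%. For normal differences the chance of a rise is Φ(0.597) = 0.725, which gives power 67%. Wilcoxon signed-rank (exact size 4.9%) has 78% and paired t 80%.

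**3. Conover across all four samples** (t on 69 df, critical value 1.995). With venous and cupping levels similar, simulated power is about 71% at size 5%. With the two kinds of blood 4-8 noise SDs apart, simulated size is about 14-15% and power about 79-81%.

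The limiting case shows why. If one kind of blood always takes ranks 1-2 and the other 3-4, and the other pair is evenly split, |t| = |2b − n| / √[(2n² − (2b − n)²)/(3(n − 1))]. At b = 16 this is 8/√(1088/69) = 2.01, p = 0.048. The test now rejects from 16 of 24, and 2 × P(B ≥ 16 | p = 0.5) = 15.2%. Requiring a significant overall Friedman test first would not protect, because the separation itself makes that test significant.

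**4. The whole rule on the two-sample reading** (paired t if both samples pass, otherwise 17 of 24). Power with skewed people and normal differences, 60,000 trials per setting:

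| Person log-SD | Fixed paired t | Rule, plain K-S | Rule, Lilliefors | Wilcoxon |
|---|---|---|---|---|
| 0.5 | 80% | 80% | 74-75% | 78% |
| 0.8 | 80% | 78% | 70% | 78% |
| 1.0 | 80% | 76% | 68-69% | 78% |

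The loss against paired t is 0-4 points (plain) or 5-12 points (Lilliefors). At log-SD 0.3 it is about 0 and 2 points. The size of the rule stays at 4.7-6.4%.

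**5. Strongly skewed pairs.** With lognormal pairs (correlation 0.5, log-SD 0.8), raw paired t has 63%, the rule 67-68%, Wilcoxon 73%, and paired t on logs 80%. At log-SD 1.0 the figures are 55%, 67%, 71% and 80%.

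**The case against.** Much of the defence stands.

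- A reader might infer that the fallback certainly counts only rises. It does so only if Conover means the post-Friedman comparison and only if it is run on two samples. The SAP states neither, and with four samples per person a multi-sample run is a natural reading.
- A reader might also treat Friedman as the plan's paired fallback. The SAP names it in the Student's t sentence; only Conover is set against paired t.
- The SAP names Kolmogorov-Smirnov without a correction, so the 0-4 point loss belongs to the test as named. The 5-12 points apply only if the version used is Lilliefors-corrected.
- The larger losses need wide spread: log-SD 0.8 and 1.0 mean between-person coefficients of variation of √(e^0.64 − 1) = 95% and √(e − 1) = 131%. The participants are healthy volunteers and the documents give no spread.
- The phrase about the data could include differences. That makes the check unclear rather than certainly misdirected.
- The rule is also silent when one sample of a pair passes and the other fails. This adds little on the two-sample reading: even taking whichever test is significant gives a size of at most 7.3% in the settings tried.
- Wilcoxon is not free of assumptions. With skewed differences whose median is zero it rejects about 11-13% of the time, where the rise count stays at 6.4%. With heavy-tailed differences a sign-type test can be slightly more powerful (Laplace 67% against 63%).

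None of this supplies the missing definition or directs the check at the differences.

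**Conclusion.** The point holds. The check is not tied to the quantity on which the paired t-test depends, and the fallback is undefined. On either way of running the post-Friedman comparison, it serves a two-sample contrast less well than a direct analysis of the change.

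Two summaries are tempting, and the documents support neither. One is that the cost is simply lost power. That fits the two-sample reading (67% against 78-80% within the fallback; 0-4 or 5-12 points for the whole rule at log-SD 0.5-1.0). It fails on the four-sample reading with well-separated levels, where the harm is a size of about 14-15%. The other is that the plan inflates false positives in general. On the two-sample reading it does not do so materially.

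Every power figure rests on assumed distributions, because the documents give none. The dependence on rises alone, the 17-of-24 threshold and the 6.4% size are exact, given the stated meaning of Conover, two samples and no ties. The SAP should be changed before analysis; confidence in the practical size of the harm is moderate.

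**What to change.** For the before/after contrasts, drop the group-level normality check and the Conover/Friedman branch. Prespecify one analysis of the within-person change for each marker, using only the two samples compared. Possible wording:

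*For each marker, the within-person change (venous: after the third session minus initial; cupping blood: third session minus first) will be tested with a two-sided Wilcoxon signed-rank test and reported as the Hodges-Lehmann estimate (pseudomedian) with its 95% CI. A paired t-test, on a raw or log scale fixed for each marker before the data are seen, is the sensitivity analysis. No normality test selects the analysis.*

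The reverse order, with paired t primary on the pre-fixed scale, is equally acceptable. A raw-scale t-test should not be the automatic choice: for the strongly skewed pairs in step 5 it loses 73 − 63 = 10 to 71 − 55 = 16 points against Wilcoxon. If a normality check is kept, apply it to the differences, with Wilcoxon as the fallback.

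The cost is SAP wording only. Wilcoxon gives up about 2 points against paired t when differences are normal. It assumes roughly symmetric differences, so it should not be described as a test of the median change. A sign-type test may do slightly better if differences are heavy-tailed.

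### Four markers are each tested at p<0.05 with none named primary and no adjustment, so an efficacy statement can rest on the best of four results

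*SAP*

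**What the plan says.** The title of both documents announces the "Efficacy of Wet Cupping on Reactive Oxygen Species and Antioxidant Capacity". The Protocol's sampling paragraph first describes "venous blood samples obtained initially and after the completion of the three consecutive application". It then adds cupping blood: "In addition samples from the cupping blood during the first and the third WCT application will also be obtained". On the measurements it says: "Total antioxidant status(TAS),total oxidant status (TOS),super oxide dismutase (SOD),catalase (CAT) levels will be measured biochemically in all samples". It does not rank the four markers.

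The SAP is a single paragraph under Statistical Analysis. It chooses tests by a normality check. Its first pair of tests is Student's t-test or, failing normality, Friedman: "Friedman test will be used for groups showing abnormal distribution". For paired groups it gives the paired t test or, failing normality, Conover: "for groups showing abnormal distribution Conover test will be used". It does not say that Conover is read only after a significant Friedman test. It closes with one threshold, p<0.05, which "will be accepted as statistically significant".

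Neither document names a primary marker, a primary comparison, a testing order or a multiplicity adjustment, and neither calls any analysis exploratory.

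**The concern.** The order of the sampling paragraph suggests that the venous before-after change is the main comparison, although the Protocol does not say so. The ambiguity that matters most is therefore among the four markers. Under the rule as written, a venous p-value below 0.05 on any one marker could be presented as evidence of efficacy, and nothing fixed in advance would say whether that was the marker meant to count.

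What is at stake is how far such a statement can be believed. A single significant result out of four carries less weight than the same result on a marker chosen beforehand, and a reader of the report could not tell the two apart.

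**Working it through.** The documents give no power figure, familywise rate or effect size, so there is no figure of theirs to reproduce.

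**Inputs from the documents**
- Threshold per test: 0.05 (SAP, Statistical Analysis).
- Markers: 4 (Protocol, measurement sentence).
- Venous comparisons: 1 before-after comparison per marker, so 4 tests.
- Sample size: "24 individuals were enrolled in the study" (Protocol, opening paragraph).

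**Assumptions**
- Tests are two-sided; the SAP does not say.
- Every pair of markers has the same correlation r between their changes. The documents give no value, so a range is shown.
- No marker truly changes.

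**Step 1: paired t branch, independent markers.** 1 − (1 − 0.05)^4 = 1 − 0.8145 = 0.1855, or 18.5%.

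**Step 2: paired t branch, correlated markers.** For four z tests with common correlation r and c = 1.96, the chance of at least one p<0.05 is

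1 − ∫ φ(x) · [Φ((c − √r·x)/√(1−r)) − Φ((−c − √r·x)/√(1−r))]^4 dx.

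A simulation of four paired t tests with n = 24 checks this. The Holm column is from simulation.

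| r | z integral | simulated paired t | Holm across four |
|---|---|---|---|
| 0 | 18.5% | 18.6% | 4.9% |
| 0.3 | 17.4% | 17.4% | 4.7% |
| 0.5 | 15.6% | 15.8% | 4.4% |
| 0.7 | 13.0% | 13.3% | 3.8% |
| 0.8 | 11.4% | 11.6% | 3.3% |
| 0.9 | 9.4% | 9.4% | 2.7% |

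Repeat simulations at r = 0.9 gave 9.4% to 9.6%, hence about 9.5%. Relative to a single test this is 18.5/5 = 3.7 times at r = 0, 13/5 = 2.6 times at 0.7 and 9.5/5 = 1.9 times at 0.9.

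**Step 3: non-normal branch, Conover read without a gate.** With four samples per person and all four markers judged non-normal, the simulated chance of at least one false venous before-after result is 18.6% at r = 0, 18.1% at 0.3, 17.2% at 0.5 and 15.3% at 0.7. That is about 15% to 19%.

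**Step 4: non-normal branch, Conover read only after Friedman p<0.05.** The SAP does not state this gate. The figures assume r from 0 to 0.7 and a correlation of 0.2 to 0.8 between the samples of one person.
- No samples differ: about 6% to 8%.
- Cupping and venous blood differ by 0.5 SD, venous unchanged: about 14% to 22%.
- Cupping and venous blood differ by 1 SD, venous unchanged: about 17% to 29%.

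A real difference between the two kinds of blood makes Friedman significant. The gate then no longer protects the venous before-after comparison. Such a gate would in any case cover only markers judged non-normal.

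**Step 5: price of Holm.** Its strictest step is 0.05/4 = 0.0125. With n = 24 and a paired t test at 80% power, the detectable within-person change is 0.597 SD of the differences at 0.05 and 0.732 SD at 0.0125. Power for 0.597 SD at 0.0125 is 59%.

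**The case against.** The strongest reply is that the SAP only defines when a p-value is called significant. It does not say that one significant marker establishes efficacy. The study is small and self-controlled, its markers are few and named in advance, and reporting four unadjusted p-values is a common convention in such work. This stands in part: a reader might infer that the plan declares an any-one-of-four success rule or breaks a promised 5% familywise rate, and it does neither. The reply does not remove the problem, because the title says efficacy and neither document calls the analysis exploratory.

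A reader might also infer that the four markers carry equal weight. The documents say only that all are measured. One could argue that TAS and TOS, listed first, are the global measures closest to the title. A family of two would give 1 − 0.95^2 = 9.75%. That ranking is not stated either; what the text supports is that no marker is named primary.

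Thirdly, 13% to 18.5% might be read as the error rate of the plan as a whole. It belongs to the paired t branch with correlations up to 0.7. Higher correlations lower it, ungated Conover tests give about 15% to 19%, and a Friedman gate could bring it to 6% to 8% when no samples differ. The SAP leaves open which case applies.

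Finally, counting the cupping-blood first-versus-third comparisons as well would make eight tests and 19.1% to 33.7% at correlations of 0.7 to 0. The Protocol presents cupping blood as an addition, so the four venous tests are the fairer count for the efficacy question.

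**Conclusion.** The concern holds as a matter the sponsor should correct. With a flat 0.05 threshold, four markers and none named primary, the chance of at least one false venous before-after finding on the paired t branch is about 9.5% to 18.5% for assumed marker correlations of 0.9 to 0, against 5% for one test. On the non-normal branch the size depends on a gate that the SAP does not state and on assumed differences between cupping and venous blood, so those figures are illustrations only. All of them assume two-sided tests and no true venous change.

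The documents do not support a finding that an error guarantee has been violated or that the data are compromised. The defect is that the plan does not say which result would answer the efficacy question.

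**What to change.** Amend the SAP before any marker result is seen. The Protocol describes enrolment and treatment in the past tense but measurement in the future, so this may still be possible. Naming a primary marker after seeing results would give no protection.

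- Name the venous before-versus-after change as the primary comparison.
- Then either name one marker as primary at 0.05 with the other three secondary, or apply Holm across the four.
- Label the cupping-blood and venous-versus-cupping comparisons exploratory, and report estimates with 95% confidence intervals.
- If no confirmatory claim is intended, label all four markers exploratory, report estimates with 95% confidence intervals, and base no efficacy conclusion on a single p<0.05.

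No option needs extra samples or participants. Naming one primary marker costs that marker no power. With Holm, at its strictest step, the change detectable at 80% power rises from 0.60 to 0.73 SD, and power for a 0.60 SD change falls from 80% to 59%. The exploratory label gives up the confirmatory claim.
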